6.5.1. Open Label / Cross over Treatment

Starting after the Week 8 visit, if disease recurrence is confirmed and the definition as described in Section 9.4.3 is satisfied, participants will cross over to open-label treatment with guselkumab. Similarly, participants who are determined to have endoscopic recurrence by central read on the Week 48 or flare visit ileocolonoscopy will also cross over to open-label treatment; for the optional Week 24 ileocolonoscopy, if the central reader confirms endoscopic recurrence (modified Rutgeerts score of i2a or greater), cross over may be done at the discretion of the principal investigator with the participant's agreement. If a participant does not cross over at Week 24 for endoscopic recurrence but, within the following 16 weeks, develops an increase in CDAI \geq 70 or meets the corticosteroid-related disease recurrence criteria (see Section 9.4.3), then the participant may cross over without the need for a repeat ileocolonoscopy.

As discussed in Section 8, at the cross over visit, participants, regardless of the treatment arm to which they were randomized, will receive guselkumab for 3 doses, followed by maintenance guselkumab This regimen matches the regimen under study in the ongoing Phase 3 study, CRD3004. The induction will be open-label and the participant and investigator will remain blinded to original randomized treatment assignment. Participants will not be allowed to cross over after the Week 128 visit and, while awaiting their confirmatory ileocolonoscopy, regularly scheduled study intervention may be held.

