A Week 48 video ileocolonoscopy will be performed between Weeks 48 and 51 and participants with endoscopic recurrence confirmed by a central reader will cross over to open-label treatment with guselkumab SC induction. An optional video ileocolonoscopy can be performed at Week 24 and cross over will occur at the discretion of the principal investigator if there is only endoscopic recurrence without disease recurrence. If participants meet criteria for disease recurrence after Week 8 they will also cross over to open-label treatment.

Participants who discontinue study intervention early will return for an early termination visit at least 12 weeks after study intervention discontinuation, which will also serve as their final safety visit. This visit will include a video ileocolonoscopy at the time of discontinuation, except those participants who have already had demonstrated endoscopic recurrence in a study ileocolonoscopy.

Database Locks and Maintenance of the Blind

The first database lock (DBL) is the main study DBL. It will occur when all participants have completed the Week 48 visit assessments, or have terminated study participation prior to Week 48, and will include all assessments performed as of that date (even those beyond Week 48). The final DBL will occur after the last participant completes the final safety visit at Week 156. Additional DBLs may be added between Weeks 48 and 156, as warranted.

The study blind will be maintained for the investigative sites, site monitors, and study participants until after the final participant has completed their Week 156 visit. In the event of an emergency, the investigator may also unblind a participant's treatment if such knowledge would change the participants' clinical care. The sponsor will remain blinded to the original treatment assignments until after the main study DBL has occurred.

Study Length

After the screening period, the total study duration is 156 weeks, with the final dose of study intervention given at Week 144 and the final efficacy visit at Week 152 followed by the final safety visit at Week 156. The end of the study is defined as when all participants have completed the Week 156 visit assessments, or have terminated study participation prior to Week 156 and had their last follow-up assessment (12 weeks after the last dose of study intervention or at early termination visit).

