5.4.1.1. Definition of Endpoint(s)

Clinical remission without disease recurrence is a composite endpoint defined by the following:

- CDAI < 150 at Week 48 and
- No endoscopic recurrence as defined by Rutgeerts score < i2a by Week 48 and
- Have not experienced a disease recurrence as defined below

Disease recurrence is a composite endpoint defined by the following:

- A ≥ 70-point increase from baseline in CDAI score at beyond 8 weeks after randomization; and a CDAI score of ≥ 200 **and** evidence of endoscopic recurrence. Endoscopic recurrence is defined as a modified Rutgeerts score of ≥ i2a at the anastomotic site or its equivalent elsewhere in the GI tract, unless a stool test for C. difficile toxin or other enteric pathogen is positive
- In event of a positive test for enteric pathogen including C. difficile toxin, the underlying infection should be treated and if ileocolonoscopy has not yet been performed, it should only be done when the infection has resolved, and if disease recurrence threshold is still met
- OR initiation of a physician-prescribed corticosteroids, or an increase in the dose of steroids already being taken (by greater than 5 mg/day), for over one week for the treatment of CD and evidence of endoscopic recurrence as described above, unless a stool test for C. difficile toxin or other enteric pathogen is positive
- OR a new draining external fistula
- OR the reopening and draining of a previously existing external fistula
- OR developing a new internal fistula
- OR developing a new perianal abscess
- OR developing a new intra-abdominal abscess more than three months after the date of the index surgery

Participants who have confirmed endoscopic recurrence without disease recurrence at Week 24 or Week 48 and cross over to open-label guselkumab treatment will be censored at cross over for the time to disease recurrence endpoint.

Abdominal pain free at Week 48 is defined as abdominal pain (AP) score = 0 at Week 48

Time-to-recurrence of symptoms is defined as time to attaining an AP mean daily score >1 (and also >1 point higher than baseline) along with stool frequency (SF) mean daily score >3 (and also >3 higher per day than baseline) for 2 consecutive weeks through Week 48. Participants who cross over to open-label guselkumab treatment and do not have recurrence of symptoms will be censored at cross over for the time to recurrence of symptoms endpoint.

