5.4.1.2.2. Estimand of Time to Disease Recurrence

Objective: To evaluate disease recurrence in participants treated with guselkumab versus placebo after surgery

Estimand Scientific Question of Interest: What is the difference in time to disease recurrence at the main database lock, and thus considered to have benefited from guselkumab versus placebo?

Study intervention:

- Experimental: Guselkumab ^{CCI} at Week 0 and then ^{CCI} at Week 8, then ^{CCI} thereafter through the end of the total study period.
- Control: Matched placebo CCI at Weeks 0 and 8 and then CCI thereafter through the end of the total study period.

Population: Participants with recent (<49 days) qualifying surgery and no evidence of active Crohn's disease postoperatively.

Variable: The time to disease recurrence (as defined above) or experiencing ICE 1-3 presented below.

CONFIDENTIAL – FOIA Exemptions Apply in U.S.

Summary Measure (Population-level summary): Difference in the time to disease recurrence (as defined above) or experiencing ICE 1-3 presented below between guselkumab group and the placebo group.

Intercurrent events and their corresponding strategies:

The following are the ICEs considered for this study:

Table 10: Intercurrent Events and Corresponding Analysis Strategies for Disease Recurrence at Main Database Lock

Int loc	ercurrent Events (between baseline and main database k)	Analysis Strategy for Intercurrent Events
1.	A CD-related surgery (with the exception of minor procedures such as drainage of a superficial abscess or seton placement, etc.)	Composite Strategy: Participants are considered having disease recurrence if they experience any of these ICEs, prior to main database lock, as
2.	A prohibited change in CD medication (details in Appendix 9 Medications of Special Interest)	reflected in the variable definition.
3.	Discontinuation of study intervention due to lack of efficacy or an AE of worsening CD	
4.	Discontinuation of study intervention due to COVID-19 related reasons (excluding COVID-19 infection)	Treatment Policy: ICE4 and ICE5 will be ignored, and any data observed after the
5.	Discontinuation of study intervention due to reasons other than those in ICE 3 or 4	associated ICE event will be used for the analysis.

Abbreviation: AE=adverse event; CD=Crohn's disease; COVID-19= Coronavirus disease 2019; ICE=intercurrent event

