Intercurrent events in categories 1 to 3 will be handled by the composite strategy. This estimand acknowledges that having an ICE in categories 1 to 3 is an unfavorable outcome. For participants experiencing ICEs in category 4 and 5, the treatment policy strategy will be used and considers the occurrence of ICE category 4 and 5 is irrelevant in defining the treatment effect and so observed values of the variable will be used, if available, regardless of the occurrence of ICE category 4 and 5.

5.4.1.2.3. Estimand of Abdominal Pain Free at Week 48

Objective: To evaluate abdominal pain scores in guselkumab versus placebo after surgery.

Estimand Scientific Question of Interest: What is the proportion of participants achieving abdominal pain free at Week 48, and thus considered to have benefited from guselkumab versus placebo?

Study intervention:

- Experimental: Guselkumab ^{CCI} at Week 0 and then ^{CCI} at Week 8, then ^{CCI} thereafter through the end of the total study period.
- Control: Matched placebo ^{CCI} at Weeks 0 and 8 and then ^{CCI} thereafter through the end of the total study period.

Population: Participants with recent (<49 days) qualifying surgery and no evidence of active Crohn's disease postoperatively.

Variable: A binary variable of abdominal pain free at Week 48 (abdominal pain [AP] score = 0) or experiencing ICEs 1-4 in Table 9.

Summary Measure (Population-level summary): Difference in proportions of the binary variable of abdominal pain free, as described above, between guselkumab group and the placebo group.

Intercurrent events and their corresponding strategies:

The same ICEs and corresponding strategies that are specified for primary endpoint of endoscopic recurrence prior to or at Week 48 will be used.

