5.4.1.2.4. Estimand of Time-to-Recurrence of Symptoms

Objective: To evaluate symptoms such as stool frequency and abdominal pain scores in guselkumab versus placebo after surgery.

Estimand Scientific Question of Interest: What is the difference in time to symptoms at the main database lock, and thus considered to have benefited from guselkumab versus placebo?

Study intervention:

- Experimental: Guselkumab ^{CCI} at Week 0 and then^{CCI} at Week 8, then ^{CCI} thereafter through the end of the total study period.
- Control: Matched placebo CCI at Weeks 0 and 8 and then CCI thereafter through the end of the total study period.

Population: Participants with recent (<49 days) qualifying surgery and no evidence of active Crohn's disease postoperatively.

Variable: The time to symptoms (defined as time to attaining an AP mean daily score >1 (and also >1 point higher than baseline) along with stool frequency (SF) mean daily score >3 (and also >3 higher per day than baseline) for 2 consecutive weeks through Week 48) or experiencing ICE 1-3 in Table 10.

Summary Measure (Population-level summary): Difference in the time to symptoms (as defined above) or experiencing ICE 1-3 presented in Table 10 between guselkumab group and the placebo group.

Intercurrent events and their corresponding strategies:

The same ICEs and corresponding strategies that are specified for second secondary endpoint of time to disease recurrence will be used.

5.4.1.2.5. Estimand of Steroid Free Clinical Remission at Week 48

Objective: To evaluate the efficacy of guselkumab treatment at Week 48 compared with placebo in limiting steroid use and maintaining remission in the postoperative period.

Estimand Scientific Question of Interest: What is the proportion of participants achieving steroid free clinical remission at Week 48, and thus considered to have benefited from guselkumab versus placebo?

Study intervention:

- Experimental: Guselkumab CCI CCI at Week 0 and then CCI at Week 8, then CCI thereafter through the end of the total study period.
- Control: Matched placebo CCI at Weeks 0 and 8 and then CCI thereafter through the end of the total study period.

Population: Participants with recent (<49 days) qualifying surgery and no evidence of active Crohn's disease postoperatively.

Variable: A binary variable of steroid free clinical remission at Week 48 (defined as CDAI <150 and no corticosteroids within 30 days) or experiencing ICEs 1-4 in Table 9.

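### Time to recurrence of symptoms censors every crossover, including the mandatory one after confirmed disease recurrence, although other clinical failures count as events for the same endpoint

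*SAP*

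**What the plan says.** **The endpoint.** SAP 5.4.1.1 requires mean daily abdominal pain above 1 and stool frequency above 3, each also exceeding baseline by a set margin, for two weeks running and no later than Week 48. It then adds: "Participants who cross over to open-label guselkumab treatment and do not have recurrence of symptoms will be censored at cross over". No reason for crossover is named, so all reasons are covered.

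**Its other events.** In SAP 5.4.1.2.4 the variable reads "for 2 consecutive weeks through Week 48) or experiencing ICE 1-3 in Table 10", and the section states: "The same ICEs and corresponding strategies that are specified for second secondary endpoint of time to disease recurrence will be used". Table 10 (SAP 5.4.1.2.2) lists non-minor CD surgery (ICE 1), a prohibited change in CD medication (ICE 2) and "Discontinuation of study intervention due to lack of efficacy or an AE of worsening CD" (ICE 3). All three are composite: "Participants are considered having disease recurrence if they experience any of these ICEs". Crossover is not in Table 10.

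**Crossover.** SAP 1.2.1 states: "If participants meet criteria for disease recurrence after Week 8 they will also cross over to open-label treatment". Protocol 6.5.1 says the same. Crossover for endoscopic recurrence alone at the optional Week 24 examination is discretionary.

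**Neighbouring endpoints.** For time to disease recurrence, SAP 5.4.1.1 censors only crossovers with endoscopic recurrence and no disease recurrence. For abdominal pain free (5.4.1.2.3) and steroid-free remission (5.4.1.2.5): "The same ICEs and corresponding strategies that are specified for primary endpoint of endoscopic recurrence prior to or at Week 48 will be used". Under that set, crossover is ICE 4 and counts as failure. Protocol 9.4.3 says only that the remaining time-to-event endpoint is handled much like time to disease recurrence. It does not state the wider censoring rule.

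**The concern.** Two participants can fail in much the same way and be scored differently. One stops drug for lack of efficacy and is an event. The other meets confirmed disease recurrence, must cross over, and becomes a non-event on the crossover date.

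For time to disease recurrence the problem does not arise, because disease recurrence is itself the event and only endoscopic-only crossovers are left to censor. The symptom endpoint takes over that ICE table but has a different event, and its censoring sentence lacks the limit to crossovers without disease recurrence.

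The log-rank test and Cox model treat censoring as unrelated to prognosis. Here it follows clinical worsening, and it should be commoner on placebo if the drug works. At stake are events and power at test 5. Because testing is hierarchical, failure at test 5 also closes test 6.

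**Working it through.** **1. Does disease recurrence imply the symptom event?** No.
- A new or reopened draining fistula, or an abscess, needs no change in pain or stools (SAP 5.4.1.1).
- On the CDAI route, the weights in SAP Appendix 12 give pain a factor of 5 on its 7-day sum. Daily pain rising from 0 to 2 adds 2 × 7 × 5 = 70 points with stool frequency unchanged. That meets the 70-point rise. If CDAI also reaches 200 and endoscopic recurrence is confirmed, disease recurrence is met while the joint pain-and-stool rule is not.

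**2. Which crossovers are lost?**
- *Steroid route:* normally already an event. SAP Appendix 9 makes starting oral steroids, or raising them above baseline, for worsening CD an ICE 2 change for all estimands.
- *Non-minor CD surgery:* ICE 1. *Antibiotics started or changed for worsening CD:* ICE 2.
- *Symptom rule met before crossover:* already an event.
- *Left over:* CDAI-plus-endoscopy, fistula and abscess routes with no ICE 1-3 event.
- Crossover after the Week 48 ileocolonoscopy falls at or beyond the endpoint's horizon and matters little.

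**3. The plan's nearest figure.** No power is stated for the symptom endpoint. For time to disease recurrence, SAP Table 6 gives 90.0% (20% v 10%, 185 per arm).
- HR = ln(0.9)/ln(0.8) = 0.472.
- Exponential hazards set at Week 48, accrual 25%/35%/40% over 18 months, total 30 months and 15% annual dropout give 81.6 expected events.
- Freedman: z = √81.6 × (1 − 0.472)/(1 + 0.472) − 1.96 ≈ 1.28, power 90.0%.
- Schoenfeld: z = (√81.6/2) × |ln 0.472| − 1.96 ≈ 1.43, power 92.4%.
- Mean follow-up: 0.25 × 27 + 0.35 × 21 + 0.40 × 15 = 20.1 months, against about 20 stated.

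The stated figure is reproduced with the rates read as Week 48 rates.

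**4. Balance between arms.** 185 × 0.20 = 37 placebo and 185 × 0.10 = 18.5 guselkumab disease recurrences, a ratio of 2:1. Only the part left over in step 2 is censored.

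**5. Illustration of size.** This is a log-rank simulation over 48 weeks with 185 per arm, 4,000 runs, 15% annual dropout and crossover possible after Week 8. Assumptions not in the documents: the symptom rates; the share q of planned disease recurrences that reach crossover with no symptom or ICE 1-3 event; and independence of crossover and symptoms.

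| Symptom rates, placebo/guselkumab | Crossover censored | Crossover counted, q = 25% / 50% / 75% |
|---|---|---|
| 20%/10% | power about 73%, HR about 0.48 | power 82% / 88% / 92%, HR about 0.49 |
| 10%/5% | power about 41%, HR about 0.50 | power 57% / 70% / 80%, HR about 0.50 |
| 10%/10% | HR 1.00 | HR 0.84 / 0.75 / 0.69 |

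Mean crossovers censored as non-events, placebo v guselkumab: about 8 v 4 (q = 25%), 15 to 16 v 8 (50%) and 23 to 24 v 12 (75%).

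With symptom rates of 20%/10%, power under censoring barely moves with q (73.8%, 73.8%, 72.4%). What is forgone is therefore mainly the crossover events themselves.

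**The case against.** The strongest reply is that a symptom endpoint should stay about symptoms. Disease recurrence is already an event at test 3, so these failures are not lost to the hierarchy. The 10%/10% row above shows the cost of the alternative: counting crossovers gives an apparent benefit with no symptom difference. That cost is real and has to be reported. It does not settle the matter, because the endpoint is already a failure composite through ICE 1-3. Stopping for lack of efficacy counts with no symptom requirement, so excluding crossover for confirmed recurrence departs from the plan's own logic, and no reason is given.

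A second reply is that binary and time-to-event endpoints may handle crossover differently. The SAP does so elsewhere: endoscopic-only crossover is failure at tests 1 and 2 and censored at test 3. This stands. Scoring the same crossover as failure at tests 4 and 6 but censoring it at test 5 is not by itself an error.

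A third reply is timing. Censoring is at crossover, which on the CDAI route follows stool testing, ileocolonoscopy and central reading (Protocol 6.5.1 and Section 8). Some participants will complete the two-week rule in that interval. This also stands, and it is one reason the affected share is unknown.

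A reader might infer that every disease-recurrence crossover is lost. Appendix 9 and ICE 1 show otherwise.

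**Conclusion.** The concern holds for crossovers by the CDAI-plus-endoscopy, fistula or abscess routes without an ICE 1-3 event. For these the censoring is likely informative, and it is expected to be unequal by arm, about 2:1 at the planned disease-recurrence rates. Nothing else in the documents corrects it.

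The supported consequence is loss of events and power. A reader might go further and infer bias toward no effect. The documents do not establish that. If crossover is independent of symptoms, the hazard ratio is unchanged. The contrast moves toward the null only if those crossing over were nearer to symptom recurrence. A reader might also want one figure for the power lost. None is available, because no symptom rates are stated and the affected share is unknown. The comparison of about 73% with 82% to 92% is an illustration under the assumptions in the working.

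The effect is confined to test 5 and access to test 6. The primary result and tests 2 to 4 do not depend on it. SAP Section 1 records that the study stopped after four participants and that the planned analyses are kept for reference, so the defect is in the plan and no result rests on it.

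**What to change.** In SAP 5.4.1.1 and 5.4.1.2.4:

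- List crossover after disease recurrence as a composite event on the crossover date, in line with ICE 1-3.
- Limit censoring to crossovers for endoscopic recurrence without disease recurrence, as for time to disease recurrence.
- Report the present censoring rule as a sensitivity analysis.
- Report the symptom-only component beside the composite, so that a difference carried by crossovers without pain or stool symptoms can be seen.

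The cost is SAP wording and one extra analysis, with no new data. The downside is a broader endpoint that can show a treatment difference without a symptom difference, which is why the symptom-only component is needed.

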5.4.1.2. Estimand(s)

5.4.1.2.1. Estimand of Clinical Remission without Disease Recurrence at Week 48

Objective: To evaluate clinical remission without disease recurrence in participants treated with guselkumab versus placebo after surgery.

Estimand Scientific Question of Interest: What is the proportion of participants achieving clinical remission without disease recurrence at Week 48, and thus considered to have benefited from guselkumab versus placebo?

Study intervention:

- Experimental: Guselkumab ^{CCI} at Week 0 and then ^{CCI} Week 8, then ^{CCI} thereafter through the end of the total study period.
- Control: Matched placebo CCI at Weeks 0 and 8 and then CCI thereafter through the end of the total study period.

Population: Participants with recent (<49 days) qualifying surgery and no evidence of active Crohn's disease postoperatively.

Variable: A binary variable of clinical remission without disease recurrence at Week 48 (as defined by Rutgeerts score smaller than i2 and CDAI <150 without disease recurrence) or experiencing ICEs 1-4 presented below.

Summary Measure (Population-level summary): Difference in proportions of the binary variable of clinical remission without disease recurrence, as described above, between guselkumab group and the placebo group.

Intercurrent events and their corresponding strategies:

The ICEs considered for this study are listed in Table 9:

Table 9:	Intercurrent Events and Corresponding Analysis Strategies for Clinical Remission without	t
	Disease Recurrence at Week 48	

Int	ercurrent Events (between baseline and Week 48)	Analysis Strategy for Intercurrent Events
1. 2.	A CD-related surgery (with the exception of minor procedures such as drainage of a superficial abscess or seton placement, etc.)A prohibited change in CD medication (details in Appendix 9 Medications of Special Interest)	Composite Strategy: Participants are considered not achieving clinical remission without disease recurrence if they experience any of these ICEs, prior to Week 48, as reflected in the variable definition.
3.	Discontinuation of study intervention due to lack of efficacy or an AE of worsening CD	
4.	Cross over to open-label guselkumab	
5. 6.	Discontinuation of study intervention due to COVID-19 related reasons (excluding COVID-19 infection) Discontinuation of study intervention due to reasons other than those in ICE 3 or 5	Treatment Policy: ICE5 and ICE6 will be ignored, and any data observed after the associated ICE event will be used for the analysis.

Abbreviation: AE=adverse event; CD=Crohn's disease; COVID-19= Coronavirus disease 2019; ICE=intercurrent event

Intercurrent events in categories 1-4 will be handled by the composite strategy. The composite strategy assesses the treatment effects not only based on the variable measurements, but also based on ICEs. This estimand acknowledges that having an ICE in categories 1-4 is an unfavorable outcome. For participants experiencing ICEs in category 5 and 6, the treatment policy strategy will be used and considers the occurrence of ICE category 5 and 6 is irrelevant in defining the treatment effect and so observed values of the variable will be used, if available, regardless of the occurrence of ICE category 5 and 6.

